6.3.2.2 MBS Freedom at 2 Hours Postdose

MBS freedom at a single time point postdose is defined as the MBS reported on study before dosing that is absent at that time point, e.g., subjects who report nausea as the MBS on study before dosing and have nausea absent at 2 hours postdose. The MBS on study before dosing is reported as nausea, phonophobia, or photophobia. Symptom status is reported postdose as present or absent for each symptom (nausea, phonophobia, and photophobia).

For the co-primary endpoint, subjects who meet both of the following criteria are classified as responders:

- MBS reported on study before dosing that is absent at 2 hours postdose, i.e., in the 2-hour postdose analysis window
- No rescue medication taken at or before the 2 hours postdose, i.e., (1) rescue medication start date/time missing or (2) rescue medication start date/time > {eDiary finding date/time for the MBS status assessment in the 2-hour postdose analysis window}.

Subjects who have any of the following are classified as failures:

- MBS missing on study before dosing (see Section 7.5.2)
- Rescue medication taken at or before 2 hours postdose (RM=F), i.e., (1) rescue medication start date/time \leq {eDiary finding date/time for MBS status assessment in the 2-hour postdose analysis window}, or (2) (rescue medication start date/time – study drug start date/time) \leq 135 minutes, the upper bound of the 2-hour postdose analysis window (see Section 7.3) if MBS status is missing in the 2-hour postdose analysis window
- MBS present at 2 hours postdose, e.g., nausea reported as MBS on study before dosing and nausea present in the 2-hour postdose analysis window
- MBS missing at 2 hours postdose (NC=F), e.g., nausea reported as MBS on study before dosing and nausea status missing in the 2-hour postdose analysis window.

Main Analyses

MBS freedom outcomes at 2 hours postdose are tabulated by treatment group (see Section 6.3.4.1). Outcomes are tabulated analogously for each subgroup level of all efficacy subgroups of interest specified in Section 4.3 plus MBS on study before dosing (nausea, phonophobia, photophobia).

The percentages of subjects with MBS freedom at 2 hours postdose are compared between zavegepant and placebo using CMH tests stratified by IWRS prophylactic migraine medication use at randomization (yes, no). In these analyses, the NC=F and RM=F methods are applied. The same statistics are tabulated as those for the main analysis of pain freedom at 2 hours postdose (see Section 6.3.2.1). The stratified percentage difference between each zavegepant treatment group and placebo is tested at an alpha level of 0.05. Zavegepant is considered to be superior to placebo for this co-primary endpoint if the p-value for the stratified percentage difference is < 0.05 .

The main analysis is repeated unstratified for each subgroup level of all efficacy subgroups of interest specified in Section 4.3 plus MBS reported on study before dosing (nausea, phonophobia, photophobia).

Sensitivity Analyses

Sensitivity analyses include the following:

- Complete cases: The main analysis is repeated using NC=M, i.e., subjects who have missing MBS status in the 2-hour postdose analysis window are excluded. First, subjects whose MBS on study before dosing is missing are classified as failures. Next, the RM=F method of handling rescue medication use is applied. Finally, subjects with missing MBS status in the 2-hour postdose analysis window are excluded.
- Multiple imputation: The main analysis is repeated using the copy from reference multiple imputation approach with $m=20$ imputations to impute missing MBS status in the 2-hour postdose analysis window. First, subjects whose MBS on study before dosing is missing are

classified as failures. Next, the RM=F method of handling rescue medication use is applied. Finally, missing response status (responder versus failure) in the 2-hour postdose analysis window is imputed.

- Varying response rate imputation: The main analysis is repeated by imputing missing MBS at 2 hours postdose in each treatment group with varying response rates over the range of 0%, 10%, 20% and 30%. First, subjects whose MBS on study before dosing is missing are classified as failures. Next, the RM=F method of handling rescue medication use is applied. Finally, missing response status (responder versus failure) in the 2-hour postdose analysis window is imputed.

See Section 6.3.2.1 for additional details about methods and the presentation of statistics.

6.3.3 Secondary Efficacy Endpoints

All secondary efficacy endpoints are evaluated for the efficacy analysis set, unless specified otherwise.

If the co-primary endpoint tests are both significant for zavegepant versus placebo, then the secondary endpoints are tested for zavegepant versus placebo using a hierarchical gate-keeping procedure, with each test in the hierarchy conducted at $\alpha=0.05$. The endpoints are tested in the order shown in Section 3.1.2.

A by-subject listing of outcomes for pain relief, return to normal function, phonophobia freedom, photophobia freedom, and nausea freedom is provided for the randomized analysis set at each time point postdose. The listing also includes IWRS prophylactic migraine medication use at randomization and time to rescue medication start date/time in minutes (see Section 6.3.3.8), as well as functional disability level, phonophobia status, photophobia status, and nausea status at the time of dosing. See Section 6.3.4.1 for efficacy outcomes over time.

6.3.3.1 Pain Relief at 15 Minutes, 30 Minutes, 60 Minutes, and 2 Hours Postdose

Pain relief at a single time point postdose is defined as a pain intensity of none or mild at that time point.

Pain relief outcomes at 2 hours postdose are tabulated by treatment group (see Section 6.3.4.1).

At each time point postdose (15 minutes, 30 minutes, 60 minutes, and 2 hours), treatment group comparisons of the percentage of subjects with pain relief use analogous methods as the main analysis of the co-primary endpoint of pain freedom with NC=F and RM=F (see Section 6.3.2.1).

6.3.3.2 Return to Normal Function at 15 Minutes, 30 Minutes, 60 Minutes, and 2 Hours Postdose

Return to normal function at a single time point postdose is defined as a functional disability level of normal at that time point for subjects with functional disability at the time of dosing. Functional disability is defined as a functional disability level of mildly impaired, severely

impaired, or requires bedrest. Thus, all analyses of return to normal function are based on the efficacy analysis set with functional disability at the time of dosing (see Section 7.5.2).

Return to normal function outcomes at 2 hours postdose are tabulated by treatment group (see Section 6.3.4.1).

At each time point postdose (15 minutes, 30 minutes, 60 minutes, and 2 hours), treatment group comparisons of the percentage of subjects with return to normal function use analogous methods as the main analysis of the co-primary endpoint of pain freedom with NC=F and RM=F (see Section 6.3.2.1).

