5 SAMPLE SIZE, POWER, AND TYPE 1 ERROR

It is anticipated that about 90% of the 700 subjects randomized to each treatment group will have a headache in the allotted time period, resulting in approximately 630 subjects evaluable for efficacy in each treatment group.

The sample size calculation is based on results from the Phase 2/3 dose-ranging study BHV3500-201. The response rates for the pooled zavegepant 10 mg and 20 mg groups, and for the placebo group in study BHV3500-201 were 22.8% and 15.5%, respectively, for pain freedom at 2 hours postdose, and 42.2% and 33.7%, respectively, for MBS freedom at 2 hours postdose.

A total sample size of 1,260 evaluable subjects (630 per treatment group) provides approximately 91% power for the co-primary endpoint of pain freedom at 2 hours postdose, approximately 88% power for the co-primary endpoint of MBS freedom at 2 hours postdose, and approximately 80% power to detect a difference between treatment groups for both endpoints jointly.

Type I error is controlled by a hierarchical gate-keeping procedure. First, the family of 2 co-primary endpoints is tested. In particular, zavegepant is tested for superiority against placebo at an alpha=0.05 level for both co-primary endpoints. If the tests of both co-primary endpoints are significant (i.e., both p-values are ≤ 0.05), then the secondary endpoints are tested hierarchically at the alpha=0.05 level in the order shown in the Section 3.1.2, using the efficacy analysis set. Thus, a secondary endpoint is tested only if the preceding secondary endpoint in the hierarchy is determined to be significant (i.e., p-value ≤ 0.05). If a test in the hierarchy is not significant, then any further tests on endpoints in the sequence have p-values presented only for descriptive purposes, and no conclusions are drawn from those results.

For exploratory endpoints, no attempt is made to adjust for multiplicity. Any exploratory endpoints for which p-values are produced are evaluated at an unadjusted, 2-sided alpha=0.05 level and presented only for descriptive purposes.

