6.3 Efficacy

Efficacy analyses are based on the efficacy analysis set by as-randomized treatment group only (excluding overall).

Treatment comparisons of binary endpoints are stratified by IWRS prophylactic migraine medication use at randomization except within subgroups. If a single cell has sparse data (< 5 subjects), then the analysis is performed pooled across strata.

All CIs are 2-sided. In treatment comparisons of binary endpoints, CIs are based on a normal approximation to the binomial distribution using asymptotic standard error (ASE). In descriptive analyses of binary endpoints, exact Clopper-Pearson CIs are used. Otherwise, CIs for continuous endpoints are based on the normal distribution.

Postdose efficacy data are slotted into analysis windows automatically by the eDiary (see Section 7.5.2). All efficacy endpoints are assessed using analysis windows, unless specified otherwise.

Methods of handling missing data in analyses of binary efficacy endpoints are defined as follows:

- Non-Completer = Failure (NC=F): Subjects with missing data at a single time point are classified as failures. This missing data imputation method is applied to endpoints based on data from a single time point (e.g., co-primary endpoints) as the main analysis method.
- Non-Completer with Missing Data at More than 1 Time Point = Failure (NC1=F): Subjects with missing data at > 1 time point postdose in a specified time period are classified as failures. This missing data imputation method is applied to endpoints that are based on data

from multiple time points (e.g., secondary endpoint of sustained pain freedom from 2 to 24 hours postdose) as the main analysis method.

- Non-Completer = Missing (NC=M): Subjects with missing data at a single time point are excluded from the analysis. This missing data exclusion method is applied to endpoints based on data from a single time point (e.g., co-primary endpoints) as a sensitivity analysis.
- Multiple imputation (see Section 6.3.2.1). This missing data exclusion method is applied only to the co-primary endpoints as a sensitivity analysis.
- Varying response rate imputation (see Section 6.3.2.1). This missing data exclusion method is applied only to the co-primary endpoints as a sensitivity analysis.

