The percentages of subjects with pain freedom at 2 hours postdose are compared between zavegepant and placebo using Cochran-Mantel-Haenszel (CMH) tests stratified by IWRS prophylactic migraine medication use at randomization (yes, no). In these analyses, the NC=F and RM=F methods are applied. The following statistics are presented:

- Response rate (i.e., “n/N” and percentage), ASE, and 95% CI by randomization stratum for each treatment group
- Response rate (i.e., “n/N” and percentage), ASE, and 95% CI for each treatment group
- Percentage difference between treatment groups (zavegepant – placebo), ASE, 95% CI, and p-value by randomization stratum
- Stratified percentage difference between treatment groups (zavegepant – placebo), ASE, 95% CI, and p-value.

The stratified percentage difference between zavegepant and placebo is tested at an alpha level of 0.05. Zavegepant is considered to be superior to placebo for this co-primary endpoint if the p-value for the stratified percentage difference is < 0.05.

The main analysis is repeated unstratified for each subgroup level of all efficacy subgroups of interest specified in Section 4.3.

Sensitivity Analyses

Sensitivity analyses include the following:

- Complete cases: The main analysis is repeated using NC=M, i.e., subjects who have missing pain intensity in the 2-hour postdose analysis window are excluded. First, the RM=F method of handling rescue medication use is applied. Next, subjects with missing pain intensity in the 2-hour analysis window are excluded. The same statistics as the main analysis are tabulated.

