7.5.2 Migraine Characteristics

The following migraine characteristics are collected on study (i.e., on or after the randomization date) (1) before or at the time of dosing in the eDiary Migraine Report and (2) postdose from 15 minutes through 48 hours (e.g., 15, 30, 45, 60, and 90 minutes; 2, 3, 4, 6, 8, 24 and 48 hours) in the eDiary Postdose Migraine Report:

- Pain intensity (none, mild, moderate, severe)
- MBS (nausea, phonophobia, photophobia) before dosing in the eDiary Migraine Report only
- Nausea status (present, absent)
- Nausea intensity (mild, moderate, severe), if nausea status is present
- Phonophobia status (present, absent)
- Phonophobia intensity (mild, moderate, severe), if phonophobia status is present
- Photophobia status (present, absent)

- Photophobia intensity (mild, moderate, severe), if photophobia status is present
- Functional disability level (normal, mildly impaired, severely impaired, requires bedrest)
- Aura (yes, no) preceding or accompanying headache before dosing in the eDiary Migraine Report only.

The eDiary allows subjects to report one result per time point per migraine characteristics parameter.

In general, if subjects answered “no” to taking study medication mistakenly already, had current pain intensity of moderate or severe before dosing, and did not use other headache medications, then the eDiary Migraine Report collects current levels of all parameters on study before dosing and at scheduled postdose time points.

Otherwise, if subjects answered “yes” to taking study medication mistakenly already and provided the time of study medication taken, then the eDiary Migraine Report collects all parameters listed above (1) retrospectively at the time of dosing except MBS and aura, and (2) prospectively at scheduled postdose time points (as applicable based on study medication time).

For analyses, migraine characteristics collected in the eDiary Migraine Report are considered to be “at the time of dosing”, except MBS and aura, which is considered to be “on study before dosing”.

Windows for postdose efficacy measurements (15, 30, 45, 60, 90 minutes; 2, 3, 4, 6, 8, 24, and 48 hours) are automatically assigned by the eDiary as shown in [Table 5](#).

Table 5: eDiary Automated Efficacy Analysis Windows

Postdose Evaluation	Analysis-Specified Interval	Target Time
15 minutes	10 to 20 minutes	Study medication start time + 15 minutes
30 minutes	25 to 35 minutes	Study medication start time + 30 minutes

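### The test of return to normal function does not use the level of disability at dosing; if that level is prognostic, power at secondary endpoint 2, which gates endpoints 3 to 17, is lower than it could be

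*SAP*

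**What the plan says.** SAP 6.3.3.2 covers return to normal function at 15, 30 and 60 minutes and 2 hours (secondary endpoints 14, 12, 10 and 2). It states that "treatment group comparisons of the percentage of subjects with return to normal function use analogous methods as the main analysis" of pain freedom. That analysis, in SAP 6.3.2.1, uses CMH "tests stratified by IWRS prophylactic migraine medication use at randomization (yes, no"). SAP 6.3 sets the same single stratification factor for all binary treatment comparisons and pools over strata when a cell has fewer than 5 subjects.

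Disability before dosing has one role in the test: "all analyses of return to normal function are based on the efficacy analysis set with functional disability at the time of dosing". The eDiary records it on four levels, "Functional disability level (normal, mildly impaired, severely impaired, requires bedrest") (SAP 7.5.2), and three of these remain in the subset. Subjects with a normal or missing level are not evaluable (SAP 6.3.4.1), so the level is complete for everyone analysed. No adjusted or sensitivity analysis by level is planned.

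SAP 5 makes the secondary endpoints a fixed sequence: "a secondary endpoint is tested only if the preceding secondary endpoint in the hierarchy is determined to be significant". Function at 2 hours is second in that sequence, after the co-primary pair and pain relief at 2 hours. SAP 5 gives power for the co-primary endpoints only.

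**The concern.** Response means reaching the top category of a four-point scale. A mildly impaired subject has one step to go and a subject who requires bedrest has three. The dosing-time level is therefore the baseline of the outcome, and baseline values often predict such outcomes. When they do, a test that stratifies on them removes between-subject variance that the planned test keeps.

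The position of endpoint 2 raises the stakes. If it misses p ≤ 0.05, the 15 endpoints from 3 to 17 carry p-values for description only. Endpoints 10, 12 and 14 come late in the sequence, so much less depends on them.

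**Working it through.** **1. The plan's own figures.** Inputs from SAP 5: 630 per group; 22.8% v 15.5% (pain freedom); 42.2% v 33.7% (MBS freedom); alpha 0.05, taken as two-sided.

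Power = Φ[(d − 1.96·se0)/se1], with se0 = √(2p̄(1−p̄)/n) and se1 = √((p1(1−p1)+p2(1−p2))/n).

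- Pain freedom: d = 0.073, se0 = 0.02217, se1 = 0.02208, giving Φ(1.34) = 91.0%.
- MBS freedom: 87.6%.
- Product: 79.6%.

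These match the stated 91%, 88% and 80%. One-sided 0.05 would give 95.1% and 92.9%, which does not match.

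**2. Return to normal function, with marginal rates held fixed.** The documents supply none of the inputs, so all are assumptions: 567 per arm impaired at dosing (90% of 630); level mix 50/30/20% (mild/severe/bedrest); rates 30% v 38%; a common odds ratio across levels.

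- *Without level:* p̄ = 0.34, se0 = √(0.4488/567) = 0.02813, se1 = √(0.4456/567) = 0.02803. Power = Φ[(0.08 − 0.05514)/0.02803] = Φ(0.887) = 81.2%.
- *With level:* replace each variance by its average within levels. For the strong gradient (placebo 43.6/20.3/10.4%, active 53.6/27.6/14.7%), se0 = √(0.4030/567) = 0.02666 and se1 = √(0.3995/567) = 0.02654. Power = Φ[(0.08 − 0.05225)/0.02654] = Φ(1.045) = 85.2%.

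| Gradient | Relative odds of response by level | Placebo rates (%) | Power with level | Gain over 81.2% (points) | Gain across five rate pairs* |
|---|---|---|---|---|---|
| None | 1/1/1 | 30/30/30 | 81.2% | 0 | 0 |
| Weak | 1/0.75/0.55 | 34.2/28.1/22.3 | 81.7% | 0.4 | 0.4–0.5 |
| Moderate | 1/0.5/0.33 | 38.7/24.0/17.2 | 82.8% | 1.6 | 1.3–1.8 |
| Strong | 1/0.33/0.15 | 43.6/20.3/10.4 | 85.2% | 4.0 | 3.2–4.6 |
| Very strong (mix 40/35/25) | 1/0.25/0.10 | 51.0/20.7/9.4 | 87.4% | 6.1 | 5.1–7.2 |

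*25 v 32, 25 v 33, 30 v 37, 30 v 38 and 33.7 v 42.2%.

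Simulating the CMH test itself at 30% v 38% (4,000 trials each, two strata against six, 14% assumed on prophylaxis) gave 81.2% to 81.3% (none), 81.3% to 82.4% (moderate) and 82.0% to 86.0% (strong). Type I error was 4.6% to 5.4% for both tests.

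**3. A second set of assumptions, with the odds ratio held fixed.** Mix 45/35/20%, odds ratio exp(0.40), 15% on prophylaxis, 567 per arm, 4,000 trials each.

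| Placebo rates by level (%) | Prophylaxis only | Plus three levels | Plus two levels (severe and bedrest combined) |
|---|---|---|---|
| 30/24/20 | 85.6% | 85.8% | – |
| 38/20/12 | 82.5% | 85.1% | 84.6% |
| 45/15/6 | 73.1% | 79.7% | 79.3% |
| 52/10/3 | 61.9% | 75.7% | 75.4% |

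The fall down the second column is largely a shrinking marginal difference: 34.2 − 25.9 = 8.3 points in the first row, 33.7 − 27.5 = 6.2 in the last. With the difference held at 8.3 points, the large-sample gains are about 0, 2, 5 and 9 points.

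**4. 15 minutes.** At assumed rates of about 4 to 6% the gain was essentially nothing, and at most about 2 points.

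**5. Sparse cells.** Bedrest by prophylaxis holds 567 × 0.20 × 0.15 ≈ 17 subjects per arm. Expected placebo responders there are 17 × 0.20 = 3.4, 17 × 0.12 = 2.0, 17 × 0.06 = 1.0 and 17 × 0.03 = 0.5 in the four scenarios. If a cell means stratum by arm by response, at least one of the 24 cells fell below 5 in 90 to 100% of simulated trials, and the rule in SAP 6.3 would pool everything. Combining the two worse levels helps but does not settle it: expected placebo responders on prophylaxis in the combined level are 567 × 0.15 × (0.35 × 0.15 + 0.20 × 0.06) ≈ 5.5 in the third scenario and 567 × 0.15 × (0.35 × 0.10 + 0.20 × 0.03) ≈ 3.5 in the fourth.

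**The case against.** The strongest reply is that nothing is broken. The planned test holds its type I error, stratifies by the randomisation factor and follows one rule for every binary endpoint. That stands.

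The second reply is that a loss of power is not shown, because the documents do not say how well level predicts response. That also stands. A reader might infer that power is definitely lost at all four time points; the documents do not support this, since the loss is zero if level is not prognostic and the early time points gain little. Nor does the plan disregard baseline disability, because disability defines the subset. The gain of about 14 points in the last simulated row should not be taken as typical: it needs a 52% v 3% gradient and is partly the smaller marginal effect.

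Third, the change reaches beyond SAP 6.3.3.2. Protocol 9.3.1.2 promises the co-primary statistics for secondary endpoints, SAP 6.3 fixes the stratification for all binary comparisons, and SAP 6.3.4.4 compares return to normal function at every time point by the pain-freedom method. Editing one section alone would give one endpoint two p-values. This shapes the remedy without removing the case for it.

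Last, for subjects who dosed before using the eDiary, the level is recalled after dosing (SAP 7.5.2). Their number is unknown. The planned subset already depends on the same recalled value.

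**Conclusion.** The point holds as an optional, conditional efficiency gain. The test of return to normal function is valid but leaves out the level of the outcome's own baseline. If level is prognostic, power at endpoint 2 is below what the same data could give. Under the assumptions above, the gain is about 0 points with a weak gradient, 1 to 3 with a moderate one and roughly 4 to 7 with a strong one; the lowest single strong-gradient figure is 3.2. Only extreme gradients give more.

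These figures rest on assumed subset size, level mix, prophylaxis share, response rates and gradients, none of which the documents give. The stated co-primary power is reproduced and is not affected.

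**What to change.** Before unblinding:

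- In SAP 6.3.3.2, stratify the CMH comparison and the matching stratified difference for return to normal function at 2 hours, and for consistency at 60 minutes, by prophylactic use (yes, no) and disability level at dosing. Use either mildly impaired against severely impaired or requires bedrest, or all three levels. The two-level form kept nearly all the simulated gain.
- In SAP 6.3, define a cell. State that for this endpoint sparse cells lead first to pooling over prophylactic use and do not remove the disability-level stratification.
- Use the same analysis for those time points in SAP 6.3.4.4, and note the exception to the general stratification in SAP 6.3 and Protocol 9.3.1.2.
- Keep the prophylaxis-only test as a sensitivity analysis.
- Say how subjects with a recalled level are handled.

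No new data are needed. The cost is a few sentences in the SAP, a note against the protocol, four or six strata in place of two, and small cells in the prophylaxis stratum. There is little or no return if level turns out to be weakly prognostic.
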